**Reverse cumulative distribution curves**

Reverse cumulative distribution (RCD) curves for antibody concentrations will be plotted: the x-axis represents the antibody concentrations value (log-10 scale), while the y-axis the percentage of subjects having a log-transformed antibody value greater or equal to the corresponding x-value.

**5.3.2.2. Analysis of CMI response**

The frequency of **antigen-specific** CD4+ or CD8+ T-cells for each individual subject is calculated as the difference between the frequency of CD4+ or CD8+ T-cells producing at least 2 activation markers among CD40 Ligand (CD40L), IL-2, TNF- $\alpha$ , IFN- $\gamma$ , IL-13 and IL-17, upon *in vitro* stimulation with the antigen (induction condition) minus the frequency of CD4+ or CD8+ T-cells producing at least 2 activation markers upon *in vitro* stimulation in medium only (background condition). For descriptive statistics purposes, differences less or equal to zero (0) are imputed to 1.

**CONFIDENTIAL**209538 (NTHI MCAT-009)  
Statistical Analysis Plan Amendment 2**5.4. Analysis of safety and reactogenicity****5.4.1. Analysis of safety and reactogenicity planned in the protocol**

All safety analyses will be performed on the solicited safety set, unsolicited safety set and exposed set.

Endpoint	Statistical analysis methods
Secondary	
Within group assessment
 
The percentage of subjects with at least 1 local adverse event (AE) (solicited and unsolicited), with at least 1 general AE (solicited and unsolicited) and with any AE during the 7-days solicited follow-up period and the 30-days follow-up period will be tabulated by group with exact 95% CI after each NTHi-Mcat vaccine dose and overall. The percentage of NTHi-Mcat doses followed by at least 1 local AE (solicited and unsolicited), by at least 1 general AE (solicited and unsolicited) and by any AE will be tabulated by group with exact 95% CI. The same calculations will be performed for AEs rated as Grade 3, for AEs causally related to vaccination and Grade 3 AEs causally related to vaccination.
 
The percentage of subjects reporting each individual solicited local and general AE during the 7-days solicited follow-up period after each dose of NTHi-Mcat vaccine will be tabulated by group with exact 95% CI. The percentage of NTHi-Mcat doses followed by each individual solicited local and general AE will be tabulated by group with exact 95% CI.
 
Fever will be reported per 0.5°C cumulative increments.
 
For all solicited symptoms, the same tabulation will be performed for Grade 3 AEs.
 
The verbatim reports of unsolicited symptoms will be reviewed by a physician and the signs and symptoms will be coded according to the Medical Dictionary for Regulatory Activities (MedDRA) Dictionary for Adverse Event Terminology. The percentage of subjects with at least 1 report of unsolicited adverse event classified by the MedDRA and reported up to 30 days after NTHi-Mcat vaccinations will be tabulated by group with exact 95% CI. The same tabulation will be performed for Grade 3 unsolicited adverse events, for unsolicited adverse events with a causal relationship to vaccination and for Grade 3 AEs causally related to vaccination.
 
The number of subjects who experienced any serious adverse event (SAE) or any potential immune-mediated disease (pIMD) from Day 1 to Day 331 and from Day 331 to Day 661 will be reported.
 
The number of subjects who experienced any AE leading to study withdrawal, from first vaccination up to study conclusion, or any SAE related to study participation or concurrent GSK medication/vaccination, during the entire study period, will be reported.
 
A summary of subjects reporting concomitant medication/product will be provided.

**5.4.2. Additional considerations****5.4.2.1. Analysis of solicited AEs**

The analysis of solicited AEs will be performed on the Solicited safety set.

The maximum intensity of local injection site redness/swelling will be scored at GSK Biologicals as follows:

Grade 0: <20 mm diameter

Grade 1: ≥20 mm to ≤50 mm diameter

Grade 2: >50 mm to ≤100 mm diameter

Grade 3: >100 mm diameter

**CONFIDENTIAL**209538 (NTHI MCAT-009)  
Statistical Analysis Plan Amendment 2

Temperature (i.e. fever) will be scored at GSK Biologicals as follows:

- Grade 0:  $<37.5^{\circ}\text{C}$
- Grade 1:  $37.5^{\circ}\text{C}$  to  $37.9^{\circ}\text{C}$
- Grade 2:  $38.0^{\circ}\text{C}$  to  $38.9^{\circ}\text{C}$
- Grade 3:  $\geq39.0^{\circ}\text{C}$

Fever, defined as a body temperature of  $\geq37.5^{\circ}\text{C}$  irrespective of route of measurement, will be integrated to the summaries as a general AE.

In addition, body temperature will be broken down into  $0.5^{\circ}\text{C}$  increments:

- $<36.0$
- $36.0 - 36.4$
- $36.5 - 36.9$
- $37.0 - 37.4$
- $37.5 - 37.9$
- $38.0 - 38.4$
- $38.5 - 38.9$
- $39.0 - 39.4$
- $39.5 - 39.9$
- $\geq40.0$

Compliance of subjects in completing solicited AEs information will be reported as the percentage of subjects completing at least 80% of the diary entries related to local and general solicited AEs.

#### **5.4.2.2. Analysis of unsolicited AEs**

The analysis of unsolicited AEs will be performed on the Unsolicited safety set.

Analysis of unsolicited AEs will be also stratified on AEs with a causal relationship to NTHi-Mcat vaccination.

#### **5.4.2.3. Combined analysis of solicited and unsolicited AEs**

The combined analysis of solicited and unsolicited AEs will be performed on the Unsolicited safety set.

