8. STUDY ASSESSMENTS AND PROCEDURES

(Amended 18 May 2020)

Study procedures and their timing are summarized in the SoA (Section 2).

Protocol waivers or exemptions are not allowed unless necessary for the management of immediate safety concerns.

Immediate safety concerns should be discussed with the sponsor immediately upon occurrence or awareness to determine if the subject(s) should discontinue study treatment.

Adherence to the study design requirements, including those specified in the SoA, is essential and required for study conduct.

All screening evaluations must be completed and reviewed to confirm that potential subjects meet all eligibility criteria. The investigator will maintain a screening log to record details of all subjects screened and to confirm eligibility or record reasons for screening failure, as applicable.

Procedures conducted as part of the subject's routine clinical management (e.g. blood count) and obtained before signing of ICF may be utilized for screening or baseline purposes provided the procedure met the protocol-specified criteria and was performed within the time frame defined in the SoA.

8.1. *Study procedures during special circumstances*

During special circumstances (e.g., COVID-19 pandemic), the specific guidance from local public health and other competent authorities regarding the protection of individuals' welfare must be applied. For the duration of such special circumstances, the following measures may be implemented for enrolled participants:

- *Safety follow-up may be made by a telephone call, other means of virtual contact or home visit, if appropriate.*
- *Diary cards may be transmitted from and to the site by electronic means and or conventional mail.*

CONFIDENTIAL209538 (NTHI MCAT-009)
Protocol Amendment 1 Final

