## 4. ANALYSIS SETS

### 4.1. Definition

Analysis Set	Description
Enrolled	All subjects who signed informed consent
Exposed (ES)	All subjects who received at least 1 dose of the study treatment. The allocation in a group is done in function of the administered treatment.
Full analysis (FAS)	All subjects who received at least 1 dose of the study treatment and have post-vaccination immunogenicity data
Modified full analysis (mFAS)	All subjects who received full study treatment course to which they are randomized and have post-vaccination immunogenicity data
Per protocol (PPS)	All subjects who received full study treatment course to which they are randomized and have post-vaccination data (mFAS) minus subjects with protocol deviations that lead to exclusion
Unsolicited safety	All subjects who received at least 1 dose of the study treatment  (exposed set) that report unsolicited AEs or that report not having unsolicited AEs
Solicited safety	All subjects who received at least 1 dose of the study treatment  (exposed set) who have solicited safety data

 Study treatment refers to the NTHi-Mcat vaccine. Please refer to Section 4.1.1 for additional details.

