**CONFIDENTIAL**

209538 (NTHI MCAT-009)  
 Statistical Analysis Plan Amendment 2

Code 1150 will be attributed to subjects if all the following conditions are met: subject did not complete the safety assessment following the 7-day follow-up period after NTHi-Mcat vaccinations (i.e. phone contacts), did not return the pDiary, did not return for the scheduled visit 30-days after the NTHi-Mcat vaccinations and did not report any unsolicited AE.

Code 1070.a will be used to identify subjects eliminated from the Unsolicited Safety Set by visit when the NTHi-Mcat vaccination is not administered at that visit.

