#### **4.2.5.1.2. *Solicited safety set***

Code 1030.b (not administering any NTHi-Mcat vaccine), code 800 (fraudulent data) and code 900 (invalid informed consent) and code 1160 (no post-vaccination solicited safety data) will be used to identify subjects eliminated from the solicited safety set.

Code 1070.a will be used to identify subjects eliminated from the Solicited Safety Set by visit when the NTHi-Mcat vaccination is not administered at that visit.

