#### **10.1.2.3. Daily recording of solicited symptoms**

##### ***10.1.2.3.1. Studies with paper diaries***

Denominators for the summary of local (or general) solicited symptoms will be calculated using the number of subjects who respond “Yes” or “No” to the question concerning the occurrence of local (or general) symptoms.

When a specific symptom is marked as having not occurred following a specific vaccination (i.e. SDTM CE.CEOCCUR=N for the specified post-vaccination period for the symptom in question), all daily measurements will be imputed as Grade 0.

When a specific symptom is marked as having occurred following a specific vaccination (i.e. SDTM CE.CEOCCUR=Y for the specified post-vaccination period for the symptom in question), any missing daily recordings will be given imputed values to allow them to contribute to the ‘Any’ rows but not to specific grade rows of the symptom summary tables.

When the occurrence of a specific symptom is not present (i.e. SDTM CE.CEOCCUR is neither Y nor N for the specified post-vaccination period for the symptom in question) but the group of symptoms (local or general) is marked as having occurred (i.e. SDTM CE.CEOCCUR=Y), all missing daily recordings will be given imputed values to allow them to contribute to the ‘Any’ rows but not to specific grade rows of the symptom summary tables.

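### Combined solicited-plus-unsolicited AE rates use the Unsolicited safety set with no rule for missing solicited data, so they are biased downward by about q × (P − u)

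*SAP*

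**What the plan says.** SAP Section 5.4.2.3 fixes the population for the combined table: "The combined analysis of solicited and unsolicited AEs will be performed on the Unsolicited safety set". SAP Section 4.1 admits to that set exposed subjects "that report unsolicited AEs or that report not having unsolicited AEs", which requires no diary. The exclusion code in SAP Section 4.2.5.1.1 is a joint condition: "Code 1150 will be attributed to subjects if all the following conditions are met: subject did not complete the safety assessment", and the remaining conditions are "did not return the pDiary, did not return for the scheduled visit 30-days after the NTHi-Mcat vaccinations and did not report any unsolicited AE". One completed call, or one visit, keeps the subject in.

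The solicited tables work differently. In SAP Section 4.2.5.1.2, "code 1160 (no post-vaccination solicited safety data) will be used to identify subjects eliminated from the solicited safety set", and SAP Section 10.1.2.3.1 adds "Denominators for the summary of local (or general) solicited symptoms will be calculated using the number of subjects who respond" Yes or No to the symptom question. That rule is written for solicited summaries. SAP Section 10.1.3.7, on combining solicited and unsolicited events, gives counting rules only and does not mention missing solicited data. Code 1070.a removes a subject by visit when an NTHi-Mcat dose is not given. No code removes a dose that was given but has no solicited data.

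Protocol Section 10.3.5 lists the combined rates (any, local and general, after each dose, overall and per dose administered, then Grade 3 and related) under the secondary safety analysis. It names three safety sets without assigning one to this table.

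**The concern.** The combined numerator draws on solicited events, while the denominator includes subjects and doses for which no solicited data exist. Unless a rule says otherwise, such a subject adds to the denominator and can add to the numerator only through an unsolicited event. A subject with one of two diaries is treated the same way in the row for the missing dose. The combined rates are then too low by an amount that grows with the share of missing solicited data. The related rows are affected too, because SAP Section 5.4.2.3 counts every solicited AE as causally related.

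Two things are at stake. The report may contradict itself: a combined local rate should not fall below the rate of one of its own solicited components, but with two different denominators it can. And if solicited data are lost unequally across groups, descriptive comparisons between the time-lag groups and the control would mix reactogenicity with data loss.

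**Working it through.** The documents state no AE rate and no diary-loss rate, so there is no plan figure to reproduce. The check is algebra with assumed ranges.

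**Inputs**
- Denominator rule: SAP Sections 5.4.2.3, 4.1 and 4.2.5.1.1.
- Group size for the count example: 135 (Protocol Section 5.2, Table 7).
- Assumed: true rate of any solicited AE, s = 50–90%; unsolicited rate, u = 10–30%; share without solicited data, q = 2–20%. Solicited and unsolicited events are taken as independent, and missingness as unrelated to reactogenicity.

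**Formula**
- True combined rate: P = 1 − (1 − s)(1 − u).
- Rate obtained by default: (1 − q) × P + q × u, since a subject without solicited data can still contribute an unsolicited event.
- Bias: −q × (P − u), where P − u = s × (1 − u).

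At the low end (s = 50%, u = 30%), P = 65% and P − u = 35%. At the high end (s = 90%, u = 10%), P = 91% and P − u = 81%.

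| q | Any-AE bias (points) | Local-AE bias (points), unsolicited local events taken as about nil: −q × s |
|---|---|---|
| 2% | −0.7 to −1.6 | −1.0 to −1.8 |
| 10% | −3.5 to −8.1 | −5.0 to −9.0 |
| 20% | −7.0 to −16.2 | −10.0 to −18.0 |

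The same formula serves the Grade 3 and related rows with their own P and u. Where those rates are lower, the bias in points is smaller.

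**Count example (local AE).** Of 135 subjects, 14 have no solicited data and 97 of the other 121 have an event. The combined table gives 97/135 = 71.9%. Among those with solicited data the rate is 97/121 = 80.2%.

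**Unequal loss, if it occurred.** With equal true rates, q = 2% in one group and 10% in another, the spurious difference is (0.10 − 0.02) × (P − u): 0.08 × 35% = 2.8 points to 0.08 × 81% = 6.5 points. Taking P directly as 70–90% with the same u gives 0.08 × 40% = 3.2 to 0.08 × 80% = 6.4 points.

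**Where unequal loss could arise.** Protocol Table 3 has diaries returned at Visits 4 and 6. Its Amendment 1 footnote allows V6_3, V4_6 and V6_6 to become remote contacts; V4_3 and the Sh_NTHi-Mcat_1 return visits do not carry it. In Table 4 the control group's return visits do not carry the corresponding footnote either. Protocol Section 8.1 adds: "Diary cards may be transmitted from and to the site by electronic means and or conventional mail". A substitute call avoids code 1150, while the diary then has to arrive by another route.

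**The case against.** The case against is substantial, and most of it limits the point.

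- No text says that a missing diary is scored as no event. That is correct: it is the default result of the named denominator and silence on missing solicited data. The table shells are filed elsewhere and may say more.
- A reader might infer that nothing is known about a subject who took the call but returned no diary. The documents do not support this. Both schedules of activities mark recording of solicited AEs at the 7-day calls, and Protocol Section 12.5.8 has unreturned diaries sought by telephone or other means. Such data reduce q but do not set a denominator.
- A reader might infer that reactogenicity as a whole is understated. It is not. Individual solicited AEs are analysed on the Solicited safety set with Yes/No responders as denominator, and diary compliance is reported (SAP Section 5.4.2.1).
- A reader might infer that the 3- and 6-month groups will look less reactogenic. Amendment 1 expects disrupted visits in those groups but says nothing about diary loss, and remote transfer of diaries is meant to preserve the data. Differential bias is a possibility only.
- A cruder bias of P × q ignores the unsolicited events that are still captured. At P = 70–90% it would put the 2% versus 10% gap at 5.6–7.2 points, which is too large.
- The wider set has a merit: every recorded event counts. A complete-data overall rate would drop a subject with a recorded reaction after Dose 1 and no solicited data after Dose 2. This stands, and the fix has to allow for it.

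**Conclusion.** The point holds for the combined tables only. Followed as written, SAP Section 5.4.2.3 keeps subjects and doses without solicited data in the denominator and gives no rule for them, so the combined any, local, general, Grade 3 and related rates are biased downward by about q × (P − u). The direction rests on the default reading, in which missing solicited data contribute no event. The any-AE size, about 1–2 points at q = 2% and 3.5–8 at q = 10%, rests entirely on assumed rates and on missingness unrelated to reactogenicity; it cannot be derived from the documents. The analysis is secondary and descriptive (SAP Section 6), so no confirmatory test is affected. This is a cheap improvement worth making, not a threat to the trial's conclusions.

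**What to change.** Amend SAP Section 5.4.2.3 as follows.

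1. Compute the combined rates after each dose, and per dose administered, on Unsolicited-set subjects who also have solicited data for that dose, whether from a diary, a retrieved diary or a call.
2. Compute the overall combined rate on those with solicited data after each NTHi-Mcat dose received. Moving to the Solicited safety set alone would not be enough, because a subject with data for one of two doses would still dilute the other dose's row.
3. Keep the Unsolicited-set version as a supportive table, so that no recorded event is lost.
4. Report the number without solicited data by group and dose, so that any imbalance is visible.

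The cost is SAP wording, a slightly smaller denominator and one extra table. No new data are needed. Subjects left out of the main combined table remain in the unsolicited tables and, through the Exposed Set, in the SAE tables.

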**CONFIDENTIAL**

209538 (NTHI MCAT-009)  
 Statistical Analysis Plan Amendment 2

Solicited AEs will be coded by MedDRA as per the following codes:

Solicited symptom	Preferred Term code	Corresponding Preferred Term decode
Pain	10022086	Injection site pain
Redness	10022061	Injection site erythema
Swelling	10053425	Injection site swelling
Headache	10019211	Headache
Fatigue	10016256	Fatigue
Gastrointestinal symptoms	10017944	Gastrointestinal disorder
Myalgia	10028411	Myalgia
Chills	10008531	Chills
Fever	10037660	Pyrexia

Combined analysis of solicited and unsolicited AEs will be also stratified on AEs with a causal relationship to NTHi-Mcat vaccination (all solicited AEs are considered causally related).

#### **5.4.2.4. Analysis of SAEs and pIMDs**

The analysis of SAEs and pIMDs will be performed on the Exposed Set (ES).

Analysis of SAEs will include:

- All SAEs from Day 1 to Day 331, from Day 331 to Day 661 and from Day 1 to Day 661.
- Fatal SAEs from Day 1 to Day 331, from Day 331 to Day 661 and from Day 1 to Day 661.
- Related SAEs:
  - To any study vaccine, from Day 1 to Day 331, from Day 331 to Day 661 and from Day 1 to Day 661.
  - To the NTHi-Mcat vaccine, from Day 1 to Day 331, from Day 331 to Day 661 and from Day 1 to Day 661, from the day of the first NTHi-Mcat vaccination up to 1 month following the second dose, from the day of the first NTHi-Mcat vaccination up to 6 months following the second dose and from the day of the first NTHi-Mcat vaccination up to 12 months following the second dose (all groups except “Shingrix only”).
  - To *Shingrix* vaccine, from Day 1 to Day 331, from Day 331 to Day 661 and from Day 1 to Day 661 (all groups except NTHi-Mcat).

Analysis of pIMDs will include all occurrences from Day 1 to Day 331, from Day 331 to Day 661 and from Day 1 to Day 661.

**CONFIDENTIAL**209538 (NTHI MCAT-009)  
Statistical Analysis Plan Amendment 2**5.4.2.5. Other safety analyses**

Medications will be coded using GSKDRUG dictionary.

All collected concomitant medications and vaccinations will be listed. In addition, prior and concomitant vaccinations will be summarized. In case of pregnancies during the study, follow-up data and pregnancy outcomes will be described in detail.

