Investigator	A person responsible for the conduct of the clinical trial at a trial site. If a trial is conducted by a team of individuals at a trial site, the investigator is the responsible leader of the team and may be called the principal investigator.
	The investigator can delegate trial-related duties and functions conducted at the trial site to qualified individual or party to perform those trial-related duties and functions
Pack-years of smoking:	
Pack-years is a quantification of cigarette smoking, a way to measure the total amount a person has smoked in the course of his/ her lifetime. The number of pack-years is calculated as follows:
 
(average number of cigarettes smoked per day x number of years smoked)/ 20
 
E.g. a smoking history of 10 pack-years means having smoked 20 cigarettes per day for 10 years, or having smoked 10 cigarettes per day for 20 years.
 
Note: For the purpose of this study, pipe and/or cigar use (including cigarillos) should not be used to calculate pack-year history.

Pharmacogenomics	
The International Council on Harmonisation (ICH) E15 Guidance for Industry defines pharmacogenomics as Study of variation of DNA and RNA characteristics as related to drug or treatment response. Pharmacogenetics, which is a subset of pharmacogenomics, is “the study of variations in DNA sequence as related to drug response.” Pharmacogenomic biomarkers include germline (host) DNA and RNA as well as somatic changes (e.g. mutations) that occur in cells or tissues.
 
Pharmacogenomic biomarkers are not limited to human samples but include samples from viruses and infectious agents as well as animal samples. The term pharmacogenomic experiment includes both the generation of new genetic or genomic (DNA and/or RNA) data with subsequent analysis as well as the analysis of existing genetic or genomic data to understand drug or treatment response (pharmacokinetics, safety,

CONFIDENTIAL209538 (NTHI MCAT-009)
Protocol Amendment 1 Final

efficacy or effectiveness, mode of action). Proteomic and metabolomic biomarker research are not pharmacogenomics.

Potential Immune-Mediated Disease:

Potential immune-mediated diseases (pIMDs) are a subset of AEs that include autoimmune diseases and other inflammatory and/or neurologic disorders of interest which may or may not have an autoimmune aetiology.

Primary completion date:

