12.5.8. Detecting and recording adverse events, serious adverse events and pregnancies

A pDiary, hereafter referred to as Subject Diary will be used in this study to capture solicited and unsolicited adverse events. The subject should be trained on how and when to complete each field of the Subject Diary.

The subjects will be instructed to contact the investigator immediately should the subjects manifest any signs or symptoms they perceive as serious.

Subject Diary training should be directed at the individual(s) who will perform the measurements of adverse events and who will enter the information into the Subject Diary. This individual may not be the subject, but if a person other than the subject enters information into the Subject Diary, this person's identity must be documented in the Subject Diary. Any individual that makes entries into the Subject Diary must receive training on completion of the Subject Diary at the time of the visit when Subject Diary is dispensed. This training must be documented in the subject's source record.

CONFIDENTIAL209538 (NTHI MCAT-009)
Protocol Amendment 1 Final

At each NTHi-Mcat vaccination visit, diary cards will be provided to the subject. The subject will be instructed to measure and record the axillary body temperature, and any solicited local/general AEs (i.e. on the day of vaccination and during the next 6 days) or any unsolicited AEs (i.e. on the day of vaccination and during the next 29 days occurring after vaccination. The subject will be instructed to return the completed diary card to the investigator at the next study visit.

- Collect and verify completed diary cards during discussion with the subject on Day 121; Day 181; Day 271 (Visit 4_1, Visit 4_3, Visit 4_6), and Day 181; Day 241; Day 331 (Visit 6_1, Visit 6_3, Visit 6_6) in the Sh_NTHi-Mcat groups and on Day 31 (Visit 2) and Day 91 (Visit 4) in the NTHi-Mcat group.
- Any unreturned diary cards will be sought from the subject through telephone call(s) or any other convenient procedure.

The investigator will transcribe the collected information into the eCRF in English.

12.5.8.1. Time period for detecting and recording adverse events, serious adverse events and pregnancies

All AEs during 30 days following administration of each dose of NTHi-Mcat study vaccine (Day 1 to Day 30) must be recorded onto/into the appropriate section of the eCRF, irrespective of intensity or whether or not they are considered vaccination-related.

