The investigator will assess the maximum intensity that occurred over the duration of the event for all unsolicited AEs (including SAEs) recorded during the study. The assessment will be based on the investigator's clinical judgement.

The intensity should be assigned to 1 of the following categories:

- 1 (mild) = An AE which is easily tolerated by the subject, causing minimal discomfort and not interfering with everyday activities.
- 2 (moderate) = An AE which is sufficiently discomforting to interfere with normal everyday activities.
- 3 (severe) = An AE which prevents normal, everyday activities. Such an AE would, for example, prevent attendance at work/school and would necessitate the administration of corrective therapy.

An AE that is assessed as Grade 3 (severe) should not be confused with a SAE. Grade 3 is a category used for rating the intensity of an event; and both AEs and SAEs can be assessed as Grade 3. An event is defined as 'serious' when it meets 1 of the pre-defined outcomes as described in Section [12.5.2](#).

2. Assessment of causality

The investigator is obligated to assess the relationship between study vaccine and the occurrence of each AE/SAE using clinical judgement. In case of concomitant administration of multiple vaccines/products, if possible, the investigator should specify if the AE could be causally related to a specific vaccine/product administered (i.e. investigational, control/placebo or co-administered vaccine). When causal relationship to a specific vaccine cannot be determined, the investigator should indicate the AE to be related to all products.

Alternative plausible causes, such as natural history of the underlying diseases, concomitant therapy, other risk factors, and the temporal relationship of the event to the study vaccine will be considered and investigated. The investigator will also consult the IB to determine his/her assessment.

There may be situations when a SAE has occurred and the investigator has minimal information to include in the initial report to GSK Biologicals. However, it is very important that the investigator always makes an assessment of causality for every event prior to submission of the Expedited Adverse Events Report to GSK Biologicals. The investigator may change his/her opinion of causality in light of follow-up information and update the SAE information accordingly. The causality assessment is 1 of the criteria used when determining regulatory reporting requirements.

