## 6. ANALYSIS INTERPRETATION

[figure not shown]
Except for analysis on primary objectives, with predefined success criteria and an appropriate type I error control, comparative analyses are descriptive with the aim to characterize the difference between groups.

With respect to confirmatory analyses on primary objectives the interpretation will be done in a hierarchical manner, except if only the group Sh\_NTHi-Mcat\_1 reached the number of subjects planned in the PPS, in this case we will have only one comparison to interpret.

In case of sequential testing will be applied, each non inferiority can only be concluded if all the associated criteria are met and all previous non inferiority have been concluded (see [Figure 2](#)): starting from the 6-months lag, the 3-months NI can be achieved only if the 6-months NI is demonstrated, while the 1-month NI can be achieved only if the 6-months and 3-months NI are both demonstrated. Starting from the 3-months lag, the 1-month NI can be achieved only if the 3-months NI is demonstrated.

[figure not shown]
This sequential procedure enables to control the overall type I error below 2.5% (one-sided) [[Dmitrienko, 2009](#)].

**Figure 2 Sequence for evaluating the primary objective in order to control the overall type I error below 2.5% (one-sided) in case all groups reached the number of subjects planned in the PPS**

**CONFIDENTIAL**209538 (NTHI MCAT-009)  
Statistical Analysis Plan Amendment 2

If the per-protocol sample size is not reached in the Sh\_NTHi-Mcat\_6 group, the sequential procedure enables to control the overall type I error below 2.5% (one-sided) [Dmitrienko, 2009] will be:

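### All-cause SAEs, fatal SAEs and pIMDs are tabulated only by study day, so the groups are not shown over equal time after NTHi-Mcat; a minor gap that windows already in the SAP would close cheaply

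*SAP*

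**What the plan says.** Below, control is the NTHi-Mcat group, and Sh_1, Sh_3 and Sh_6 are the groups given NTHi-Mcat 1, 3 and 6 months after Shingrix.

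SAP 5.4.2.4 analyses SAEs and pIMDs on the Exposed Set. It lists "All SAEs from Day 1 to Day 331, from Day 331 to Day 661 and from Day 1 to Day 661", and the same three periods for fatal SAEs. Its tables for "pIMDs will include all occurrences from Day 1 to Day 331, from Day 331 to Day 661 and from Day 1 to Day 661". SAEs related to NTHi-Mcat get these periods plus three more, each starting at NTHi-Mcat Dose 1 and ending 1, 6 or 12 months after Dose 2. The middle one reads "from the day of the first NTHi-Mcat vaccination up to 6 months following the second dose".

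The protocol's secondary safety objective (Table 6) is the profile of NTHi-Mcat given 1, 3 or 6 months after Shingrix or alone. Its SAE and pIMD endpoints are Day 1–331 and Day 331–661. Protocol 10.3.5 and SAP 5.4.1 place the safety methods under a within-group heading. SAP 6 adds that, outside the primary objectives, "comparative analyses are descriptive with the aim to characterize the difference between groups".

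Some dose-anchored output of any cause does exist. Unsolicited AEs "reported up to 30 days after NTHi-Mcat vaccinations will be tabulated by group with exact 95% CI" (SAP 5.4.1). Protocol 12.5.8.1 requires that "All AEs during 30 days following administration of each dose of NTHi-Mcat study vaccine (Day 1 to Day 30) must be recorded". Protocol 12.5.8.2.2 asks for intensity "for all unsolicited AEs (including SAEs) recorded during the study", and the protocol glossary says that pIMDs "are a subset of AEs that include autoimmune diseases and other inflammatory" conditions. SAP 10.1.3.7 counts SAEs as general events in the combined AE output. An SAE or pIMD of any cause within 30 days of an NTHi-Mcat dose can therefore enter those tables, pooled with other AEs.

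**The concern.** NTHi-Mcat starts on a different study day in each group. A window fixed by study day is equal in length from randomisation but holds unequal time after NTHi-Mcat, and in the Sh groups it also holds time after Shingrix alone. Someone reading the SAE or pIMD columns for the secondary objective is comparing different amounts of post-NTHi-Mcat follow-up.

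The equal-time windows depend on the investigator judging the event related to NTHi-Mcat, and the trial is open-label. A pIMD enters them only if it is also serious and judged related. Yet Protocol 3.3.1 names vaccine-induced autoimmune disease as a theoretical risk of each vaccine, with pIMD monitoring as the mitigation. At stake is how clearly the safety description answers its own question, not any test or success criterion.

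**Working it through.** **Inputs.** NTHi-Mcat dose days come from the vaccination schedules in Protocol 5.2. Follow-up to Day 661, about 22 months, is also from Protocol 5.2: (661 − 1)/30 = 22.0, so the stated figure reproduces. All days are nominal.

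**Time in the study-day windows**

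| | Control | Sh_1 | Sh_3 | Sh_6 |
|---|---|---|---|---|
| Dose 1 day | 1 | 91 | 151 | 241 |
| Dose 2 day | 61 | 151 | 211 | 301 |
| Days after Dose 1 by Day 331 (331 − Dose 1) | 330 | 240 | 180 | 90 |
| as % of control | 100 | 73 | 55 | 27 |
| Days after Dose 1 by Day 661 (661 − Dose 1) | 660 | 570 | 510 | 420 |
| as % of control | 100 | 86 | 77 | 64 |
| Days before NTHi-Mcat (Dose 1 − 1) | 0 | 90 | 150 | 240 |
| Days beyond 12 months after Dose 2 (661 − Dose 2 − 360) | 240 | 150 | 90 | 0 |

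Day 1–661 contains the period to 12 months after Dose 2 in every group (420 days), mixed with the time in the last two rows. Check: 0 + 420 + 240 = 90 + 420 + 150 = 150 + 420 + 90 = 240 + 420 + 0 = 660.

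**Length of the windows the SAP already defines.** Dose 2 is 60 days after Dose 1 in every group, so the windows last 60 + 30 = 90, 60 + 180 = 240 and 60 + 360 = 420 days in all four. In the order control/Sh_1/Sh_3/Sh_6 they end on:

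- 1-month: Day 91/181/241/331
- 6-month: Day 241/331/391/481
- 12-month: Day 421/511/571/661

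**What the 30-day AE output covers.** 2 × 30 = 60 days: 60/90 = 67% of the 1-month window, 60/240 = 25% of the 6-month window and 60/420 = 14% of the 12-month window.

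**Illustration (assumed, not from the documents).** NTHi-Mcat adds an excess e of 0.5–2%, spread evenly over the 240 days from Dose 1, with 135 subjects per group. Shingrix adds s over Day 1–241 in the Sh groups, with s = 0 or s = e. Extra subjects in Day 1–331 = 135 × [e × min(331 − Dose 1, 240)/240 + s], with s = 0 in control.

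| e = 2%, Day 1–331 | Control | Sh_1 | Sh_3 | Sh_6 |
|---|---|---|---|---|
| s = 0 | 2.70 | 2.70 | 2.03 | 1.01 |
| s = e | 2.70 | 5.40 | 4.73 | 3.71 |

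The largest gap from control is 2.70 − 1.01 = 1.7 subjects (Sh_6) with s = 0, and 5.40 − 2.70 = 2.7 (Sh_1) with s = e. At e = 0.5% every figure is a quarter of this.

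For Day 1–661, the 240-day period ends on Day 241/331/391/481, so all of it is captured in every group. With s = 0 each group shows 2.70 and there is no distortion. With s = e the values are 1/2/2/2 times control. The 6-month window gives 1/1/1/1 with s = 0. With s = e it gives 1.00/1.63/1.38/1.00, because 150, 90 and 0 of its 240 days overlap Day 1–241 in Sh_1, Sh_3 and Sh_6.

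**The case against.** The SAP follows the protocol. The study-day windows are the protocol's endpoints, start at randomisation, have equal length and keep calendar time balanced. The safety methods are headed as within-group, and no specific between-group SAE or pIMD comparison is set out. All of this stands. A reader might infer that the tables are invalid or that the SAP departs from the protocol; the documents support neither.

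A reader might also infer that all-cause SAEs and pIMDs have no dose-anchored output. That is too strong, given the 30-day AE tables. SAP 10.1.1 and 10.1.3.5 also assign each event to a dose and derive its onset day, so individual events could be placed in time. What is missing is a separate SAE, fatal-SAE or pIMD result, and anything beyond 30 days after a dose. SAP 10.2 keeps the table list in the eTMF, which was not available, so additional planned tables cannot be ruled out.

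A further inference would be that the tables make NTHi-Mcat after Shingrix look safer. Less post-NTHi-Mcat time lowers the Sh columns, but Shingrix-period events raise them, and the documents do not give the net direction.

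Finally, the remedy adds least where the imbalance is greatest. In the Epoch 001 report only the 1-month window is complete in all groups, and existing output already covers 60 of its 90 days. The gain there is the other 30 days and the separate breakdown by event class. This stands and keeps the point minor.

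**Conclusion.** The point holds as a limit on interpretation. On the SAP text, separate results for all SAEs, fatal SAEs and pIMDs are planned only by study day, so they do not describe these events over equal time after NTHi-Mcat. The imbalance is greatest in the Epoch 001 report, where Sh_6 has 27% of control's time after Dose 1. Day 1–661 is much better, and in the illustration is undistorted if Shingrix adds nothing.

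Under the assumed excess of 0.5–2%, the largest Day 1–331 gap from control is 0.4–1.7 subjects of 135 without a Shingrix effect and 0.7–2.7 with an equal one. These sizes rest on nominal days, an even spread of excess risk and assumed rates. The analysis is descriptive, events are likely to be few, and no type I error, power or confirmatory claim is touched. Severity: minor, a cheap improvement.

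**What to change.** Keep the study-day tables. For all SAEs (with fatal SAEs as a row) and for pIMDs, add the three windows that SAP 5.4.2.4 already uses for NTHi-Mcat-related SAEs. Put the 1-month window in the Epoch 001 report and the 6- and 12-month windows in the integrated report. The 12-month window ends by Day 661 in every group, within planned follow-up, so no new data are needed and no endpoint changes.

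The cost is 2 event classes × 3 windows = 6 descriptive tables, and three limits to state with them:

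- The windows fall in different calendar periods. Study-day overlap with control's 12-month window is 330/420 = 79% in Sh_1, 270/420 = 64% in Sh_3 and 180/420 = 43% in Sh_6, and the 1-month windows do not overlap control's at all. COVID-19 may therefore affect groups unequally.
- Sh_1 and Sh_3 windows can still contain late Shingrix-period events.
- Only subjects who received NTHi-Mcat are included.

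A split by COVID-19 and a table by randomised group are optional and separate from this point.
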